#### **Off-Study Criteria**

- Screen failure including meeting one of the exclusion criteria that cannot be resolved within 6 weeks of the screening visit.
- Subject noncompliance with study procedures.
- Completed study follow-up period.
- Participant requests to be withdrawn from study.
- Investigator judgment based on subject's best medical interest.

Abbreviated Title: BGJ398 in TIO

Version Date: 21MAY2019

- Death.

### 3.10.2 Off-Study Procedure

Once the decision is made to take a patient off the study protocol, a note will be entered into CRIS. The subject(s) will be referred back to their local physician(s). With written consent from the subject(s), referring physicians will receive clinical information about the health status of subjects when they are taken off the study protocol.

## 4 CONCOMITANT MEDICATIONS/MEASURES

The patient must notify the investigational site at the time of starting any new medications he/she takes after the start of the study drug. All medications (other than study drug) administered during the study must be listed on the Concomitant Medications Form in the eCRF.

### 4.1 PERMITTED CONCOMITANT THERAPY REQUIRING CAUTION AND/OR ACTION

#### 4.1.1 Drugs that alter the pH of the GI tract

BGJ398 is characterized by pH-dependent solubility, and therefore, medicinal products that alter the pH of the upper gastro-intestinal tract may alter the solubility of both compounds, and limit bioavailability. These agents include, but are not limited to, proton-pump inhibitors (e.g., omeprazole), H2-antagonists (e.g., ranitidine) and antacids. Therefore, study drug(s) should be dosed at least 2 hours before or 10 hours after dosing with a gastric protection agent.

#### Corticosteroids

Chronic dosing of corticosteroids such as dexamethasone and prednisone is known to induce CYP3A enzymes, thereby increasing the risk of reducing drug exposure to sub-therapeutic levels. In addition, BGJ398 is an *in vitro* inhibitor of CYP3A4 and has the potential to increase the systemic exposure of corticosteroids that are metabolized by CYP3A4.

Systemic corticosteroid treatment can be used with caution.

#### 4.1.2 CYP substrates and inhibitors

BGJ398 was shown to inhibit the cytochrome p450 isoenzyme CYP3A4 in *in-vitro* assays, thus, suggesting an increased risk of drug interactions with concomitant medications that are metabolized by CYP3A4. However, such interactions have not been confirmed in patients. Therefore, investigators may administer medications that are known to be metabolized by CYP3A4. Patients must be monitored for potentiation of toxicity and may require dose titration or reduction of the CYP3A4 substrate. In particular caution is advised when substrates with a narrow therapeutic index, such as alfentanil, fentanyl, astemizole, cisapride, diergotamine, ergotamine, pimozone, quinidine, sirolimus, tacrolimus, and terfenadine need to be administered. Please refer to the following website <http://medicine.iupui.edu/clinpharm/DDIs/table.asp> for a more complete list of the substrates of CYP3A4.

Abbreviated Title: BGJ398 in TIO

Version Date: 21MAY2019

Hormonal contraceptives may be affected by cytochrome P450 interactions and are therefore not considered effective for this study when used alone. Highly effective contraception as defined in the exclusion criterion should be maintained throughout the study. Additionally, BGJ398 may increase the systemic exposure of ethinyl estradiol, so patients on oral contraception should be appropriately monitored for side effects.

BGJ398 is a reversible inhibitor of CYP2C8, CYP2C9 and CYP2C19. Permitted medications to be used with caution in this study include those that are sensitive substrates of CYP2C8, CYP2C9, CYP2C19, or those substrates that have a narrow therapeutic index. BGJ398 is a substrate of CYP3A4. Therefore moderate inhibitors and inducers should be used with caution if no other alternative is available.

#### 4.1.3 Transporter substrates

*In vitro* data show that BGJ398 is an inhibitor of BCRP. CQM157, a metabolite of BGJ398, is an inhibitor of transporters P-gp, BCRP, OATP1B1, and OATP1B3 (IC50 2-4 μM). In the absence of data confirming whether such interactions occurs in patients receiving such medications must be monitored for potential toxicity and may require dose titration or reduction of the medication.

#### 4.1.4 Anti-emetics

Anti-emetics are allowed for the treatment of nausea or vomiting. It is recommended to avoid using drugs that are known to cause QT prolongation. Note that some anti-emetics have a known risk for Torsade de Pointes, and therefore need to be used with caution. Aprepitant is both a sensitive substrate and a moderate CYP3A4 inhibitor and should be used with caution if an alternative is not available.

#### 4.1.5 QT/QTc interval prolongation or torsade de pointes medications

Medications that have the potential to prolong the QT/QTc interval or induce torsade de pointes are allowed with caution. Investigators at their discretion may co-administer such medications, as listed below, but patients should be carefully monitored. Any patient taking a concomitant medication associated with prolonged QT will obtain an EKG as an outpatient within 7-10 days after an increase in BGJ398 or the relevant concomitant medication.

- a. Class IA antiarrhythmics (e.g., quinidine, procainamide, disopyramide)
- b. Class III antiarrhythmics (e.g., sotalol, ibutilide)
- c. Class 1C antiarrhythmics (e.g., flecainide, propafenone)
- d. Antipsychotics (e.g., chlorpromazine, pimozide, haloperidol, droperidol)
- e. Antidepressants (e.g., fluoxetine, venlafaxine, tricyclic/tetracyclic antidepressants e.g. amitriptyline, imipramine, maprotiline)
- f. Opioids (e.g., methadone)
- g. Macrolide antibiotics & analogues
- h. Quinolone antibiotics (e.g., moxifloxacin, gatifloxacin)
- i. Pentamidine
- j. Antimalarials (e.g., quinine)
- k. Azole antifungals (e.g., voriconazole)

*Abbreviated Title: BGJ398 in TIO*

*Version Date: 21MAY2019*

- l. Domperidone
- m. 5-HT3 antagonists (e.g., dolasetron)
- n. Beta-2 adrenoceptor agonists (e.g., salmeterol, formoterol)

## **4.2 PROHIBITED CONCOMITANT THERAPY**

### **4.2.1 Other investigational and antineoplastic therapies**

Other investigational therapies must not be used while the patient is on the study. Anticancer therapy other than the study treatments must not be given to patients while the patient is on the study medication. If such agents are required for a patient then the patient must be discontinued from the study.

### **4.2.2 CYP inhibitors**

Strong inhibitors of CYP3A4, as listed below, are prohibited because BGJ398 is a likely substrate of this isoenzyme. Caution should be used during administration of moderate inhibitors. Please note that the list may not be comprehensive. In addition, the following food products are prohibited: Seville oranges or juice, grapefruit, grapefruit juice, grapefruit hybrids, and pomelos.

- a. Anti-fungal agents: Ketoconazole, itraconazole, fluconazole
- b. Anti-retroviral agents: Ritonavir, nelfinavir, indinavir, saquinavir, amprenavir, atazanavir, fosamprenavir
- c. Antibiotic agents: Clarithromycin, telithromycin, erythromycin
- d. Others: Aprepitant, diltiazem, verapamil, nefazodone, grapefruit juice

Patient on strong or moderate CYP3A4 inducers or inhibitors or medications that rely on CYP3A4 for metabolism, should switch whenever possible to a product with less interaction with/reliance on the pathway or patient should be on a stable dose of the medication prior to enrollment

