### **2.1.2 Exclusion criteria**

Patients eligible for this study must not meet **any** of the following criteria:

1. Have another genetic or secondary cause of hypophosphatemia.
2. History of any other malignancy that has not been cured/in remission for 5 years.
3. Patients who previously received treatment with an FGFR inhibitor other than BGJ398.
4. Current evidence of corneal or retinal disorder/keratopathy including, but not limited to: bullous/band keratopathy, corneal abrasion, inflammation/ulceration, keratoconjunctivitis, confirmed by ophthalmologic examination
5. Impairment of gastrointestinal (GI) function or GI disease that may significantly alter the absorption of oral BGJ398 (e.g., ulcerative diseases, uncontrolled nausea, vomiting, diarrhea, malabsorption syndrome, small bowel resection)
6. Patients who are currently receiving treatment with agents that are known strong inducers or inhibitors of CYP3A4 are prohibited. This includes treatment with enzyme-inducing antiepileptic drugs including carbamazepine, phenytoin, phenobarbital, and primidone.
7. Consumption of grapefruit, grapefruit juice, pomegranates, star fruits, Seville oranges or products within 7 days prior to first dose
8. Use of amiodarone within 90 days prior to first dose
9. Current use of therapeutic doses of warfarin sodium or any other coumadin-derivative anticoagulants. Heparin and/or low molecular weight heparins are allowed.
10. Insufficient bone marrow function defined as all of the following:
  - ANC <1,500/mm^3 [1.0 x 10^9/L] AND
  - Platelets < 75,000/mm^3 [75 x 10^9/L] AND
  - Hemoglobin < 10.0 g/dL
11. Insufficient hepatic and renal function defined as one of the following:
  - Total bilirubin > 1.5x ULN OR
  - AST/SGOT and ALT/SGPT > 2x ULN OR
  - Blood creatinine > 1.5xULN and/or calculated eGFR < 45 ml/min/1.73 m^2 (calculated by CKD-Epi)
12. Clinically significant cardiac disease including any of the following:
  - Congestive heart failure requiring treatment (NY Heart Association grade ≥ 2),
  - History or presence of clinically significant ventricular arrhythmias, atrial fibrillation, resting bradycardia, or conduction abnormality

*Abbreviated Title: BGJ398 in TIO*

*Version Date: 21MAY2019*

- Unstable angina pectoris or acute myocardial infarction  $\leq$  3 months prior to starting study drug
  - QTcF > 450 msec (males); > 470 msec (females)
  - History of congenital long QT syndrome

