### **4.2.3 CYP inducers**

Strong inducers of CYP3A4 are prohibited because their usage would likely decrease the exposure of BGJ398. Caution should be used during administration of moderate inhibitors.

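### The CYP3A4 rules contradict each other in two places: strong inhibitors and inducers are barred yet given a stable-dose alternative, and aprepitant is both prohibited and usable with caution.

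*Combined protocol and SAP*

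**What the plan says.** **Strong agents.** Exclusion 6 in section 2.1.2 states: "Patients who are currently receiving treatment with agents that are known strong inducers or inhibitors of CYP3A4 are prohibited". It carries no stable-dose exception. Section 4.2.2 opens in the same sense: "Strong inhibitors of CYP3A4, as listed below, are prohibited because BGJ398 is a likely substrate of this isoenzyme". Section 4.2.3 does so for inducers: "Strong inducers of CYP3A4 are prohibited because their usage would likely decrease the exposure of BGJ398". The last sentence of 4.2.2 then turns to patients taking strong or moderate inducers or inhibitors, or drugs that depend on CYP3A4. They are to change to a less interacting product where possible, "or patient should be on a stable dose of the medication prior to enrollment".

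**Aprepitant.** The prohibited list in 4.2.2 includes "Others: Aprepitant, diltiazem, verapamil, nefazodone, grapefruit juice". Section 4.1.4 says: "Aprepitant is both a sensitive substrate and a moderate CYP3A4 inhibitor and should be used with caution if an alternative is not available".

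**Azoles and macrolides.** Section 4.1.5 lists drug classes with QT or torsade risk that the investigator may co-administer with careful monitoring. Among them are "Macrolide antibiotics & analogues" and azole antifungals, with voriconazole as the example. Section 4.2.2 prohibits ketoconazole, itraconazole, fluconazole, clarithromycin, telithromycin and erythromycin by name, and warns that its list may be incomplete.

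**Moderate agents.** Section 4.1.2 asks for caution with moderate inhibitors and inducers when there is no alternative.

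**The concern.** Section 4.1.2 describes BGJ398 as a CYP3A4 substrate, and 4.2.3 expects strong inducers to lower its exposure. A drug with two statuses in the protocol is therefore a question about exposure to the study drug.

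Three things are at stake.

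- **Exposure and dose path.** Section 3.1.2 escalates from 75 to 100 to 125 mg when FGF23 is not suppressed below 100 RU/ml. The top level equals the maximum tolerated dose given in 11.1.2 (125 mg once daily, continuous). An interacting drug could change exposure at a given dose and, through FGF23, the dose itself. It would also complicate reading of the pharmacokinetic samples taken at baseline and at the 4-week and 8-week visits.
- **Foreseeable use.** Section 11.1.2 reports nausea in 31.4% and vomiting in 20.8% of earlier BGJ398 patients, so choosing an anti-emetic is an ordinary event in this trial.
- **Deviations.** Section 7.1 counts any departure from the approved protocol as a deviation, 7.2.1 requires every deviation to reach the IRB within 7 working days, and 8.1 removes patients with major deviations from the per-protocol population. Where the rules disagree, it is undefined whether use of the drug is a deviation.

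**Working it through.** There is no figure to reproduce: the point rests on no sample size, power or rate. The check is to set the rules side by side.

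| Drug or class | Rule A | Rule B | Can both be followed? |
|---|---|---|---|
| Strong inhibitors | Prohibited (exclusion 6; opening of 4.2.2) | Switch where possible, or stable dose before enrollment (end of 4.2.2) | No |
| Strong inducers | Prohibited (exclusion 6; 4.2.3) | Same sentence at the end of 4.2.2 | No |
| Aprepitant | Prohibited as a strong inhibitor (4.2.2) | Moderate inhibitor, caution if no alternative (4.1.4) | No |
| Six named azoles and antibiotics | Prohibited (4.2.2) | Their classes allowed with caution (4.1.5) | Only if 4.2.2 overrides, which is not stated |
| Moderate inducers | Caution (4.1.2) | 4.2.3 mentions moderate inhibitors only | Yes |
| Foods | Exclusion 7 list | Lists in 3.2, 4.2.2 and 11.1.5 | Yes |

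**Row 1 and row 2.** Could the closing sentence of 4.2.2 be meant for moderate agents only? No, because it names strong ones. Could it be only an instruction to change medication before entry? No, because the stable dose is offered as an alternative to changing. For strong agents it therefore describes continued use that the three prohibitions rule out.

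**Row 3.** One drug has two classifications, and each leads to a different instruction. Section 4.1.2 does not settle it, because the rule for moderate inhibitors applies only if aprepitant is one, and that is what the two sections disagree about.

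**Row 4.** The overlap is between a class and some of its members. Section 4.2.2 does not ban every azole or macrolide, and voriconazole is not on its list. Since that list is declared possibly incomplete, voriconazole's status under 4.2.2 is open rather than contradictory.

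**Row 5.** Inducers appear to be meant in the second sentence of 4.2.3. Section 4.1.2 already covers moderate inducers, so no gap results.

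**Row 6.** Pomegranates and star fruits appear only in exclusion 7. Grapefruit hybrids and pomelos appear only in the other lists. No section permits a food that another forbids.

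**Count.** Rows 1 and 2 come from one sentence, so there are two direct contradictions (that sentence and aprepitant), one unstated precedence (row 4) and two editorial points (rows 5 and 6). One affected patient would be 1/10 = 10% of the planned sample.

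**The case against.** The strongest reply is that eligibility is set by section 2.1.2 alone. The closing sentence of 4.2.2 declares nobody eligible, exclusion 6 still bars current users of strong agents, and the sentence works for moderate agents and CYP3A4 substrates. That is fair as far as it goes. A reader might infer that the same patient is eligible under 4.2.2 and excluded under 2.1.2; the documents do not support this, because 4.2.2 is not an eligibility rule. What remains is that 4.2.2 gives an instruction about strong agents, tied to enrollment, that is incompatible with its own opening and with exclusion 6.

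A second reply is that 4.1.5 screens for QT risk and 4.2.2 for CYP3A4 interaction, so a drug may pass one and fail the other, and a named prohibition naturally qualifies a class entry. This largely stands. A reader might infer that azoles and macrolides as classes are both prohibited and permitted; 4.2.2 names six agents, not the classes, and 4.1.5 names none of those six. The defect is that neither section refers to the other or states an order of precedence.

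A third reply is that the consequences are unquantified and that section 4 requires all concomitant medications to be recorded, so affected patients could be found afterwards. Both are true. Recording shows who took the drug, but not whether taking it was allowed.

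None of these replies touches aprepitant.

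**Conclusion.** The point holds for two direct contradictions: the stable-dose alternative for strong agents against three unqualified prohibitions, and the two statuses of aprepitant. The azole and macrolide entries are a missing statement of precedence. The slip in 4.2.3 and the unaligned food lists are editorial; reading either as a conflict in the rules would go beyond the text.

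The size is bounded only loosely. The documents give no exposure change and no expected number of users, so the 10% per patient shows how much one case weighs in a sample of 10 and is not a prediction. The relevance to exposure rests on the protocol's own description of BGJ398 as a CYP3A4 substrate.

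The primary analysis does not change: section 8.3 uses all treated patients and exact limits, and Table 8.4 does not depend on these rules. The exposed parts are enrolment decisions, exposure and safety, deviation reporting, and the per-protocol versions of the secondary analyses in 8.4. This should be corrected, but it does not invalidate the trial's main estimate.

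**What to change.** Reconcile exclusion 6 with sections 4.1.2, 4.1.4, 4.1.5, 4.2.2 and 4.2.3 so that each drug or class has one status, either prohibited or allowed with stated caution, preferably in a single table that the other sections cite. In particular:

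- make the closing sentence of 4.2.2 agree with exclusion 6 and with the prohibitions in 4.2.2 and 4.2.3;
- give aprepitant one classification and one status;
- state that the CYP3A4 and QT lists apply together, and which governs when they differ;
- correct the reference to moderate inhibitors in 4.2.3 if inducers were meant;
- use one food list, with its time window, in exclusion 7 and sections 3.2, 4.2.2 and 11.1.5.

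Which status each drug receives is for the investigators and the drug supplier to decide. The cost is amendment wording and the approvals that section 12 requires. No procedure, visit or analysis is added.

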### **4.2.3 CYP inducers**

Strong inducers of CYP3A4 are prohibited because their usage would likely decrease the exposure of BGJ398. Caution should be used during administration of moderate inhibitors.

### **4.2.4 Phosphorus and calcium**

Prior to initiation of BGJ398, TIO will be managed with phosphate supplements and calcitriol, with the addition of vitamin D and calcium supplements as clinically indicated. These treatments will be discontinued 3 days prior to the first dose of BGJ398. However, calcium supplements may be restarted as clinically indicated if the subject develops hypocalcemia.

### **4.2.5 Herbal medications**

Herbal preparations/medications are not allowed throughout the study. These herbal medications include, but are not limited to: St. John's wort, Kava, ephedra (ma huang), ginkgo biloba, dehydroepiandrosterone (DHEA), yohimbe, saw palmetto, and ginseng. Patients should stop using these herbal medications 7 days prior to first dose of study drug.

## 5 BIOSPECIMEN COLLECTION

- Sampling time points are detailed in schedule of events section
- The total amount of blood drawn throughout the study will be approximately 584 mL over a period of 9 months. The maximum amount of blood drawn during one study visit will be 143 mL and the maximum amount drawn over an 8-week period will be 265 mL. This amount is less than the NIH guidelines of 10.5 ml/kg/8 weeks (< 550 mL) for adults.

Drawing blood for the tests and placement of IV catheters may cause discomfort or a bruise at the injection site, and rarely, an infection may occur. Blood drawing by experienced personnel limits the risk of excessive pain, bruising and infection. Twenty-four hour blood sampling is inconvenient to the subject and will cause sleep disruption. Sampling will be done through an indwelling catheter, PICC line, or repeated venipuncture. Indwelling catheterization is associated with a very small risk of infection. No special handling instructions are needed for laboratory tests specified in schedule of events except for FGF23, which will be analyzed in [name] lab (SOP provided upon request) (Table 5.1).

Table 5.1:

Test/assay	Volume blood (approx)	Type of tube	Collection point (+/- 48hrs)	Location of specimen analysis
FGF23	4 mls	EDTA	Detailed in schedule of events	Building 30/218. [name] lab. Specimen processing per SOP #17

### 5.1 SAMPLE STORAGE, TRACKING AND DISPOSITION

Research samples collected from subjects consented to this protocol will be stored in locked freezers (at -80 C) belonging to the Craniofacial and Skeletal Diseases Branch located in Building 30 on the NIH Bethesda campus. Each research sample will be labeled with the subject ID number, collection date, and specimen type. Study staff will use a computer-based specimen tracking system the NIH NICHD Clinical Trials Database (CTDB) Tracking System accessed via secure NIH servers. The system will be used to document sample collection, notify laboratories of shipments, track shipments, and provide details on the disposition of all samples. If a patient withdraws consent the participants data will be excluded from future distributions, but data that have already been distributed for approved research use will not be able to be retrieved. The principal investigator is responsible for management of samples and data at the completion of the protocol. The PI will report destroyed samples to the IRB if samples become unsalvageable because of environmental factors (ex. broken freezer or lack of dry ice in a shipping container) or if a patient withdraws consent. Samples will also be reported as lost if they are lost in transit between facilities or misplaced by a researcher. Freezer problems, lost samples or other problems associated with samples will also be reported to the IRB and the NIDCR Clinical Director. Samples will be destroyed at the end of the protocol unless there has been IRB approval to retain them.

*Abbreviated Title: BGJ398 in TIO*  
*Version Date: 21MAY2019*

## **5.2 SAMPLES FOR GENETIC/GENOMIC ANALYSIS: NOT APPLICABLE.**

### **5.2.1 Description of the scope of genetic/genomic analysis: Not Applicable.**

### **5.2.2 Description of how privacy and confidentiality of medical information/biological specimens will be maximized: Not applicable.**

### **5.2.3 Management of Results: Not Applicable.**

### **5.2.4 Genetic counseling: Not Applicable.**

## **6 DATA COLLECTION AND EVALUATION**

### **6.1 DATA COLLECTION**

All data will be kept secure. Data collected in this study will be integrated into a study specific database using the NIH NICHD Clinical Trials Database (CTDB), a web-based electronic data capture (EDC) system compliant with Part 11 Title21 of the Code of Federal Regulations. Pre-formatted protocol specific electronic case report forms (eCRFs) as part of the database will be developed and approved by the investigational team in collaboration with the NICHD CTDB development team. Study data will be primarily extracted from in-house secured NIH medical record systems including CRIS, BTRIS and medical charts. Lab data collected outside of NIH will be confidentiality faxed to a secured private fax machine in a locked office. Paper source documentation will be kept in a locked office. The investigational staff will complete eCRFs on a rolling basis utilizing data from NIH medical record data systems, outside lab reports and paper source documents. The investigational staff will keep records of files considered source documents, including those from the hospital chart and research chart.

The PI will be responsible for overseeing entry of data into the password protected EDC system and ensuring data accuracy, consistency and timeliness. The principal investigator, associate investigators, research nurses and/or a contracted data manager(s) will assist with the data management efforts. All human subject personally identifiable information (PII) as defined in accordance to the Health Insurance Portability and Accountability Act, eligibility and consent verification will be recorded. Primary data obtained during the conduct of the protocol will be kept in secure network drives or in approved alternative sites that comply with NIH security standards. Primary and final analyzed data will have coded identifiers so that research data can be attributed to an individual human subject participant.

**End of study procedures:** Data will be stored according to HHS and FDA regulations as applicable.

**Loss or destruction of data:** Should we become aware that a major breach in our plan to protect subject confidentiality and trial data has occurred, the IRB will be notified.

